6.11. Bioanalytical and Pharmacokinetic/Pharmacodynamic Methods

The observed plasma concentrations for LY3526318 over time will be reported in tabular format using descriptive statistics and graphically using individual and mean concentration time plots. Nominal protocol time will be used for the descriptive summary and mean plot and actual time for the plots of individual data.

Additional analyses may be conducted as deemed necessary on review of the data. For example, graphical and/or model-based pharmacokinetic (PK) and PK-pharmacodynamic (PD) analyses to explore exposure-response relationships for safety and/or efficacy may be conducted. Data from this study may be pooled with data from other studies if appropriate.

6.12. Safety Analyses

The general analysis of safety has been described in the CPMP SAP version 5. However, additional ISA-specific safety considerations are described in the sections below.

6.12.1. Extent of Exposure

Duration of exposure (defined as time since first dose of study treatment to last dose of study treatment in days) to study drug will be summarized by treatment group using descriptive statistics. The summary will also include the total exposure in patient years. Extent of exposure will be reported separately for the first 4 weeks (active treatment) and the last 4 weeks (post-active treatment) of the double-blind period. All patients will receive placebo starting the day of Visit 5.

Duration of exposure (days):

For the first 4-week, active-treatment period:

= Date of last dose during the active-treatment period – Date of first dose for the active-treatment period + 1.

For the last 4-week, post-active-treatment period:

= Date of last dose during the post-active-treatment period – Date of first dose for the post-active-treatment period + 1.

Total exposure in patient years will be calculated as follows:

Total exposure in patient years = Sum of duration (days) of exposures for all patients in the treatment group/365.25

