1.3. Schedule of Activities (SoA)

This SoA shows visits and procedures unique to the intervention-specific appendix (ISA) H0P-MC-BP02 (BP02) for LY3526318. Please refer to the CPMP Master Protocol and the CLBP DSA H0P-MC-CPMP(2) SoAs for additional information.

	Randomization to ISA	Double-Blind Treatment				Early Discontinuation	Notes
	V3	V4	V5	V6	V7	ED	
Study Week	0	2	4	6	8		
Visit Window (days)		±3					
Physical examination	X		X		X	X	Symptom-directed physical exam (see Section 8.2.1) at V5, V7, and ED (if applicable).
Vital signs	X	X	X	X	X	X	At V3, vitals should be taken predose and at approximately 2 and 4 hours post dosing. At V4, V5, V6, and V7, vitals should be taken predose. Pulse rate, respiratory rate, blood pressure, and temperature taken with participant in a sitting position.
ECG			X		X	X	Single ECGs at V5, V7, and ED (if applicable).
Study intervention	X	X	X	X	X		See Section 6.1.
Intervention compliance		X	X	X	X	X	
Clinical Laboratory Tests and Sample Collection							
Hematology		X	X	X	X		
Chemistry		X	X	X	X		
Lipid panel		X	X	X	X		
Urinalysis					X		
Urine pregnancy	X	X	X	X	X	X	For all WOCBP at V3: collect sample before dosing.
Urine drug screen	X		X		X	X	See Section 5.3.2.
HbA1c	X				X	X	

	Randomization to ISA	Double-Blind Treatment				Early Discontinuation	Notes
	V3	V4	V5	V6	V7	ED	
Study Week	0	2	4	6	8		
Visit Window (days)	±3						
PK sample	X	X	X	X	X	X	At V3, samples should be taken at 2 and 4 hours (±15 minutes) post dosing. At V4, V5, V6, and V7, a sample for PK should be taken before the dose is administered; participants should be asked to refrain from taking their dose on V4-V7 until they have their clinic visit and after the blood sample is taken. The date and time of LY3526318 administration prior to the PK sampling will be recorded, i.e., the dose administered in the clinic at V3 and the last at-home dose prior to each of V4, V5, V6, and V7.
CCI							
Participant Device							
Participant returns device					X	X	If a dBM device is used, the participant will return the device to the site at V7 or ED (if applicable).

Abbreviations: **CCI**; ECG = electrocardiogram; ED = early discontinuation; HbA1c = hemoglobin A1c; ISA = intervention-specific appendix; PK = pharmacokinetic; V = Visit; WOCBP = women of childbearing potential.

2. Introduction

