5.1. Summary of Study Design

The CPMP protocol provides a summary of the overall study design for the chronic pain master protocol. ISA-specific study design is provided in the BP02 protocol.

In this ISA, patients in the LY3526318 treatment arm receive LY3526318 for the first 4 weeks of the double-blind period (active-treatment period) and switch to placebo for the last 4 weeks of the double-blind period (post-active-treatment period) starting on the day of Visit 5. Placebo patients receive placebo for the entire 8-week, double-blind period. Additional details of the study design may be found in the ERB supplement for Study BP02.

For the analyses listed in this SAP, except for treatment compliance, we define the active-treatment period and post-active treatment period as follows. The first 4 weeks of the double-blind period (active-treatment period) ends at the day of Visit 5. The last 4 weeks of the double-blind period (post-active-treatment period) begins the day after Visit 5.

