6.8. Treatment Compliance

Treatment percentage of compliance will be calculated as:

$$\frac{\text{Total pills taken} * 100}{\text{Total pills expected}}$$

with total pills taken calculated by total pills dispensed minus total pills returned. A patient is considered to be compliant for a given period if this percentage is between 80% and 120%. Treatment compliance will be reported for the first 4 weeks of the study period (Visit 3 to 5, not including the day of Visit 5) and separately for the last 4 weeks of the study period (Visit 5 to 7, including the day of Visit 5). Note that if a participant misses returning pills at Visit 4 or Visit 5, there will be an issue calculating compliance for the active-treatment period, and alternate methods for calculating compliance may be considered. For participants who discontinue early, time after the penultimate visit will be excluded for calculation of treatment compliance. For example, if a participant discontinued early at Visit 6, treatment compliance will be derived only from data collected through Visit 5. Comparisons between treatment group for treatment compliance will be performed using a Fisher’s exact test. Listings for treatment compliance of individual patients by treatment period will also be provided.

Depending on the level of observed treatment compliance, and where appropriate, sensitivity analyses of primary and key secondaries may be conducted by excluding patients with poor treatment compliance.

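### SAP 5.1 and 6.12.1 together count the Visit 5 placebo dose as active-period exposure: 29 days instead of 28 for LY3526318 participants who dose that day

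*SAP*

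**What the plan says.** SAP 5.1 sets the two periods and their scope: "For the analyses listed in this SAP, except for treatment compliance, we define the active-treatment period and post-active treatment period as follows". The boundary follows: "The first 4 weeks of the double-blind period (active-treatment period) ends at the day of Visit 5", and "The last 4 weeks of the double-blind period (post-active-treatment period) begins the day after Visit 5". The day of Visit 5 thus belongs to the active period. Compliance is the only analysis exempted.

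The same section describes the change of treatment in the LY3526318 arm, whose participants "switch to placebo for the last 4 weeks of the double-blind period (post-active-treatment period) starting on the day of Visit 5". SAP 6.12.1 repeats this for both arms: "All patients will receive placebo starting the day of Visit 5".

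SAP 6.12.1 then computes active-period exposure as "Date of last dose during the active-treatment period – Date of first dose for the active-treatment period + 1". The post-active formula has the same form, and patient-years are the summed days divided by 365.25.

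A dose is expected on the day of Visit 5. The Schedule of Activities (Protocol 1.3) marks study intervention at that visit and says that "participants should be asked to refrain from taking their dose on V4-V7 until they have their clinic visit and after the blood sample is taken". Protocol 4.1 also has participants continuing oral treatment at Visits 4 through 7.

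For compliance, SAP 6.8 draws the line a day earlier. The first 4 weeks run "Visit 3 to 5, not including the day of Visit 5", and the last 4 weeks include that day.

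**The concern.** The exposure formula depends on which doses fall inside the active period. Section 5.1 puts the day of Visit 5 inside it, while 5.1 and 6.12.1 both make that day's dose placebo. The stated rule therefore ends LY3526318 exposure on a placebo dose and leaves the first placebo dose out of the post-active period.

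Compliance follows the same switch of treatment and has a carve-out for that day. Exposure has none.

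At stake is a planned safety output, the days and patient-years of exposure during active treatment. The error always runs in the same direction for the LY3526318 arm. A programmer who follows 5.1 and one who follows the placebo sentence in 6.12.1 would also produce different tables from the same SAP.

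**Working it through.** The SAP states no exposure figure to reproduce, so the check applies its formula to the schedule.

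**Inputs**
- Visit 3 = Day 1, first dose. Visit 5 (Week 4) = Day 29 and Visit 7 (Week 8) = Day 57 on schedule. The visit window is ±3 days (Protocol 1.3), so Visit 5 falls on Day 26 to Day 32.
- Placebo starts on the day of Visit 5 (SAP 5.1 and 6.12.1).
- About 150 participants are randomized and about 85% are expected to complete the 8 weeks (SAP 5.2). The allocation ratio is redacted.
- Assumptions: dosing every day; a ratio of 1:1 or 2:1; 85% to 100% of the LY3526318 arm dosing at Visit 5, since the share reaching that visit is not given.

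**Active-period days, LY3526318 participant who doses on the day of Visit 5**

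Days = last dose date − first dose date + 1.

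| Visit 5 on | Period as in SAP 5.1 | Doses before Visit 5 only | Excess |
|---|---|---|---|
| Day 26 | 26 − 1 + 1 = 26 | 25 − 1 + 1 = 25 | 1/25 = 4.0% |
| Day 29 | 29 − 1 + 1 = 29 | 28 − 1 + 1 = 28 | 1/28 = 3.6% |
| Day 32 | 32 − 1 + 1 = 32 | 31 − 1 + 1 = 31 | 1/31 = 3.2% |

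**When the excess is not one day**
- Stopped before Visit 5, or no dose that day: the last dose in the period precedes Visit 5, so the excess is 0.
- Doses just before Visit 5 missed: the excess is larger. With a last LY3526318 dose on Day 20 and a placebo dose on Day 29, the formula gives 29 days against 20.
- Placebo arm: every dose is placebo, so the day moves from one period to the other and the total is unchanged.

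**Post-active days, on schedule**
- Last dose on Day 57: 57 − 30 + 1 = 28 as defined; 57 − 29 + 1 = 29 from the first placebo dose.
- Last dose on Day 56: 56 − 30 + 1 = 27 as defined; 56 − 29 + 1 = 28.

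**Total excess in the LY3526318 arm, at one day each**

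Excess patient-years = number dosing at Visit 5 / 365.25.

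- 1:1, arm of 75: 0.85 × 75 = 63.75 (about 64), and 63.75/365.25 = 0.17; 75/365.25 = 0.21.
- 2:1, arm of 100: 0.85 × 100 = 85, and 85/365.25 = 0.23; 100/365.25 = 0.27.

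For scale, 75 participants at 28 days give 75 × 28/365.25 = 5.75 patient-years, and 100 give 7.67.

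**The case against.** The best defence is that 6.12.1 carries its own boundary. The sentence on placebo stands just above the formulas, says when active drug stops, and can be read as ending active exposure the day before Visit 5. The account of the switch in 5.1 also has the post-active period starting on the day of Visit 5. On that reading the answer is 28 days. The formula itself, last minus first plus one, is sound, and 6.12.1 speaks of exposure to study treatment in both arms rather than of LY3526318 drug-days.

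Part of this stands: the fault lies in the period definition, not in the subtraction, and the intent was probably 28 days. But the placebo sentence does not alter a definition that 5.1 applies to everything except compliance, and no other section corrects it for exposure.

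A reader might infer three larger consequences, none of which the documents support.

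- **Every participant is affected.** Only LY3526318 participants who dose on the day of Visit 5 have excess active exposure.
- **Event rates per patient-year are about 3.4% too low (1 − 28/29).** Neither document specifies such a rate, and the master SAP (CPMP SAP version 5) is not at hand. SAP 6.12.2 starts post-treatment-emergent events after Visit 5, so events on that day count as active. A 29-day denominator would match a 29-day event window.
- **Periodic safety reports would carry too many drug-days.** The exposure outputs in SAP 6.18 are numbers of subjects exposed, overall and by age, sex and race. A one-day shift changes none of them.

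**Conclusion.** The point holds, as a minor one: the rule is wrong as written for extent of exposure. LY3526318 participants who dose on the day of Visit 5 are credited with one active-period day on which they took placebo, or more if they missed the doses just before the visit. Their post-active exposure is short by the day of Visit 5.

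The excess is 3.6% for a participant on schedule and 3.2% to 4.0% across the visit window. For the arm it is about 0.17 to 0.21 patient-years at an assumed 1:1 ratio, or 0.23 to 0.27 at 2:1. These totals rest on daily dosing, one excess day each, and 85% to 100% of the arm dosing at Visit 5.

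On the documents available, the effect is confined to the descriptive summary of days and patient-years. The efficacy analyses and adverse event counts are untouched.

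**What to change.** In SAP 5.1, extend the exception that now covers treatment compliance so that it also covers extent of exposure. In SAP 6.12.1, define the last active-period dose as the last dose before the day of Visit 5, and the first post-active dose as the first dose on or after that day. This matches the boundary in SAP 6.8.

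Leave the adverse event windows as they are.

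The cost is a sentence or two of SAP text and one date condition in the program. Dosing, visits and data collection do not change: Protocol 8.4 already has the date of the last at-home dose before Visit 5 recorded. The one small downside should be noted in the SAP: any rate per patient-year calculated later would have an adverse event window one day longer than its exposure window.

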6.12.2. Adverse Events

The general analysis of AEs has been described in the CPMP SAP version 5.

This ISA will report TEAEs for the first 4 weeks as well as post-treatment-emergent adverse events (PTEAEs) for the last 4 weeks of the double-blind period. For TEAEs in the first 4 weeks of the double-blind period (active-treatment phase), the baseline will be prior to first dose date.

A PTEAE is defined as an event that first occurs or worsens in severity after the active-treatment phase (after Visit 5) and on or before study discontinuation. The Medical Dictionary for

Regulatory Activities (MedDRA) Lowest Level Term (LLT) will be used in the post-treatment-emergent computation. The maximum severity for each LLT during the active-treatment period (Visits 3 to 5) will be used as a reference.

The baseline of PTEAE is from the first dosing date to Visit 5. The post-active-treatment phase (after Visit 5) will be included as postbaseline for this analysis. While unusual, it is possible to have a missing severity for events. For an event with a missing severity during the baseline period, it will be treated as “mild” in severity for determining post-active-treatment emergence. Events with a missing severity during the post-active-treatment period will be treated as “severe” and PTEAEs will be determined by comparing with the active-treatment period.

PTEAEs will be summarized by Preferred Term and by Preferred Term within System Organ Class in participants who received LY3526318.

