5.2. Determination of Sample Size

Approximately 150 participants will be randomized in a CCI ratio to LY3526318 and placebo, respectively. It is expected that approximately 85% of participants will complete the double-blind treatment period of the study CCI

CCI

If there is no treatment difference between placebo and LY3526318, the probability of passing the efficacy criterion specified above (that is, false positive) is less than 0.05. The simulation for the power calculation and sample size determination was carried out in Fixed and Adaptive Clinical Trial Simulator (FACTS) version 6.0.

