6.1. General Considerations

The estimand for the primary clinical question of interest has been described in the CPMP SAP version 5.

Unless otherwise specified, efficacy analyses will be conducted for the first 4 weeks of the double-blind period (active-treatment phase) and separately for the entire 8-week study. A post-active-treatment population will be used for analyses of the last 4 weeks of the double-blind period (post-active-treatment phase) and will include all patients who do not discontinue at or prior to Visit 5. For treatment-emergent adverse events (TEAEs), participants in the post-active-treatment population will be analyzed according to the treatment they receive during the active-treatment phase. Adverse event (AE) analyses will be reported for the first 4 weeks of the double-blind period (active-treatment phase) and separately for the last 4 weeks of the double-blind period (post-active-treatment phase). Some AEs may be reported for the entire 8 weeks if necessary. Laboratory, electrocardiogram (ECG), and vital sign results will be reported for the active-treatment phase and separately for the entire 8-week study.

Other general considerations for analyses are described in the CPMP SAP version 5.

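### The adverse-event summary for weeks 5-8 is specified for LY3526318 recipients, so no between-arm table is clearly planned although a concurrent placebo arm exists

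*SAP*

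**What the plan says.** SAP 5.1 has the LY3526318 arm switch to placebo at Visit 5, and for the other arm says: "Placebo patients receive placebo for the entire 8-week, double-blind period". SAP 6.12.1 confirms it: "All patients will receive placebo starting the day of Visit 5".

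SAP 6.1 defines a post-active-treatment population for analyses of the last 4 weeks, which "will include all patients who do not discontinue at or prior to Visit 5". It requires adverse-event analyses to be reported for the first 4 weeks and separately for the last 4. For TEAEs it adds that "participants in the post-active-treatment population will be analyzed according to the treatment they receive during the active-treatment phase". Output over the full period is optional: "Some AEs may be reported for the entire 8 weeks if necessary".

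SAP 6.12.2 assigns an event type to each period: "This ISA will report TEAEs for the first 4 weeks as well as post-treatment-emergent adverse events (PTEAEs) for the last 4 weeks". It defines a PTEAE without reference to arm, takes the active-treatment period as the baseline, and then specifies the table: "PTEAEs will be summarized by Preferred Term and by Preferred Term within System Organ Class in participants who received LY3526318".

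The general adverse-event analysis is deferred to CPMP SAP version 5, which is not among the documents supplied.

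**The concern.** The two sections do not lead to the same table. Section 6.1 describes a population containing both arms and a rule for splitting it by earlier treatment. That rule is needed only if both arms are tabulated. Section 6.12.2 names one arm. Because the 6.1 rule is worded for TEAEs, and 6.12.2 confines TEAEs to weeks 1-4, the rule read literally matches no weeks 5-8 table that 6.12.2 specifies. A programmer could not tell from these two sections whether a placebo column is wanted.

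Weeks 5-8 are where events on withdrawal of LY3526318, or of late onset, would appear. People with chronic pain report background events on placebo too, so a count in one arm says little about cause. The missing-severity rules in 6.12.2 add to the background: a missing severity counts as mild at baseline and as severe afterwards, and both choices make an event more likely to be classed as a PTEAE. A placebo column built with the same rules would show how much of the count arises without the drug.

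**Working it through.** **Text check.** The plan gives no figure to reproduce. The question is whether any other planned output supplies PTEAEs by arm.

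| Place | Weeks 5-8 events | By arm? | Closes the gap? |
|---|---|---|---|
| SAP 6.1, period reporting | Adverse events, last 4 weeks | Implied; grouping rule names TEAEs | Not clearly |
| SAP 6.1, 8-week output | Some adverse events | Not stated | No, optional |
| SAP 6.12.2 | PTEAEs | LY3526318 recipients | No |
| SAP 6.12.3 | TEAEs by Preferred Term | Not stated | No |
| SAP 6.17 | Listed key safety events | Not stated | No, optional |
| SAP 6.18 | Serious events, pooled with other studies | Yes | No |
| SAP 6.19 | Serious events, emergent or not; other events only if TEAEs | Yes | Serious events only, not as a separate weeks 5-8 table |
| Protocol 9.3.3 | Defers to the master protocol and the SAP | n/a | No |

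What remains without a clearly specified between-arm table is chiefly the non-serious PTEAEs.

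**Illustration of what one arm can show.** From SAP 5.2: about 150 randomised, and "It is expected that approximately 85% of participants will complete the double-blind treatment period of the study". The allocation ratio is redacted, so 1:1 and 2:1 are assumed. All event rates are assumed.

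1. Size of the post-active-treatment population. If all loss falls before Visit 5: 0.85 × 150 = 127.5, about 128. If none does: 150.
2. Arm sizes. At 1:1, 64 to 75 per arm. At 2:1, 85 to 100 on LY3526318 and 43 to 50 on placebo.
3. One arm alone, Wilson 95% interval, with p = x/n and z = 1.96: [p + z²/2n ± z√(p(1−p)/n + z²/4n²)] / (1 + z²/n).
   - 13/64 = 20.3% (12.3 to 31.7)
   - 17/85 = 20.0% (12.9 to 29.7)
   - 20/100 = 20.0% (13.3 to 28.9)
4. Difference between arms, Newcombe 95% interval. With d = p₁ − p₂ and Wilson limits l and u for each arm, the lower limit is d − √((p₁−l₁)² + (u₂−p₂)²) and the upper limit is d + √((u₁−p₁)² + (p₂−l₂)²). For 17/85 v 2/43, the Wilson interval for 2/43 is 4.7% (1.3 to 15.5). The lower limit is 15.3 − √(7.1² + 10.8²) = 2.4 and the upper is 15.3 + √(9.7² + 3.4²) = 25.6.

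| LY3526318 | Placebo | Difference, points | 95% CI |
|---|---|---|---|
| 13/64 | 13/64 | 0.0 | -14.0 to 14.0 |
| 20/100 | 10/50 | 0.0 | -14.6 to 12.5 |
| 17/85 | 2/43 | 15.3 | 2.4 to 25.6 |
| 20/100 | 3/50 | 14.0 | 1.8 to 23.7 |
| 8/85 | 2/43 | 4.8 | -7.0 to 13.5 |
| 10/100 | 3/50 | 4.0 | -7.2 to 12.4 |

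The first four rows share a LY3526318 rate of about 20%. A table showing only that column cannot tell the first two rows from the next two. The last two rows show the limit of the remedy: at lower rates the difference is imprecise even with the placebo column.

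**The case against.** The strongest reply is that the gap may not exist. Section 6.12 presents itself as additional to CPMP SAP version 5, and 6.12.2 and 6.12.3 both defer to that document. Section 6.12.2 does not say that LY3526318 recipients are the only group to be tabulated, so its table could supplement a by-arm one. This stands as a limit on the claim, which is confined to what the supplied documents clearly specify.

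A second reply is that the sections differ in terminology and do not conflict. If TEAE in 6.1 covers weeks 5-8 events, a by-arm analysis is already required. If it does not, the two sections concern different event types. This stands in part, since the grouping rule does name TEAEs. However, the population sentence in 6.1 is not limited to TEAEs, and the requirement to report adverse events separately for the last 4 weeks is not limited to one arm. Both favour a two-arm table.

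A third reply is that the registry output in 6.19 might capture non-serious weeks 5-8 events by arm if TEAE is read broadly. Section 6.12.2 ties TEAEs to the first 4 weeks, so that reading is doubtful. Even if it holds, events below a 5% threshold may be dropped and weeks 5-8 would not be shown separately.

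Finally, the matter is small and the illustrative rates are assumed; 20% would be high for a single Preferred Term and is nearer to a rate for any PTEAE. That is fair, and it limits what the figures can support.

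**Conclusion.** The concern holds. The PTEAE table is specified for LY3526318 recipients, 6.1 implies a two-arm population for the same weeks, and nothing supplied clearly specifies a between-arm PTEAE table. One descriptive safety table is affected, mainly for non-serious events; the primary conclusion is not. The illustrative intervals rest on assumed event rates and an assumed allocation ratio. They show that one arm yields no difference, and they do not size a harm in this trial. Confidence is moderate because CPMP SAP version 5 could not be checked. The change should be made because it is nearly free and the design already provides the comparator.

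**What to change.** In SAP 6.12.2, keep the two summaries (Preferred Term, and Preferred Term within System Organ Class) but replace the restriction to LY3526318 recipients with: *for the post-active-treatment population, by treatment group (LY3526318 to placebo; placebo to placebo)*, with the denominator for each arm. In SAP 6.1, make the by-treatment rule name PTEAEs as well as TEAEs. The PTEAE definition, baseline and missing-severity rules apply unchanged to both arms. A between-group difference with its interval is optional.

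If CPMP SAP version 5 already specifies a by-arm table of weeks 5-8 events, cite it in 6.12.2 instead and say that the LY3526318 summary is additional to it.

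The cost is two SAP sentences and one table column. The placebo adverse-event data are already collected.
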